Hospital/Local Health Care Referrals

Subjects will be recruited at each site from individual practice(s) of the investigators as noted above as well as faculty/resident clinics. Ongoing contact with practice and faculty members as well as with residents will be made by the investigators and coordinators, reminding them of the inclusion criteria, importance of the study, etc. In addition, the investigators will describe the study to members of other departments in the hospital, primarily family practice, medical endocrinology, and gynecology who also see and treat these patients. Contact with local physicians will be made and/or grand rounds will be given to disseminate information about the study. Letters will be mailed or emailed to potential subjects which provides details of the study and contact information of the study team (to allow for subject to reach out for more information). Penn Datastore as well as electronic medical record (EMR) recruitment tools such as SlicerDicer and best practice announcements (BPA) (and PSU, CHOP equivalents) may be utilized to provide a list of potential subjects based on clinical practice information. **COMET-PCOS PROTOCOL V10.1**

Referrals from Study Participants

Study participants often refer friends, acquaintances and colleagues to be potential participants. A subject referral-based payment structure will be added to increase recruitment. Prior study participants who have given their permission for re-contact that are not Penn Employees will be contacted to give them the opportunity to refer individuals to our study. For each individual referred who qualifies as eligible, the prior participant will get \$25. The referral period will last until the study team determines the budget to support this type of referral is no longer available. The study team will inform the prior participants at that time of the ending of the referral-based payment program.

Previous Study Participants

The trial will be offered to women who have previously participated in clinical trials offered by the study team, who have consented to be contacted for future participation via their preferred contact method (after confirmation of their potential eligibility for admission into the study based on inclusion and exclusion criteria).

Local Advertisements

Advertisements will be placed in local newspapers and run on local television networks / radio near Penn and PSU and will be continued on a regular basis if response is good. SEPTA advertising through regional rail, Market-Frankford line and Broad Street Line has been a top source of recruitment in the pass and may be utilized again.

Contact with PCOS support groups

Contact will be made with both national and local support groups to spread information about the study through informational brochures and/or participation in local meetings if necessary.

Web sites

The study will be prominently displayed on the local (Penn, PSU, CHOP) web site. Additionally, each center will have a web page devoted to this study with general as well as contact information. Information will also be available at clinicaltrials.gov. Social Media and Craigslist will also be utilized, as this has been a proven source of recruitment in the past. For ads placed on social media, specifically Facebook and Instagram, they will be one-way adds and the study team will not directly interact with subjects on social media. The ad will highlight a contact number for the interested individual to call to discuss the study. Social media ads will be monitored by the University of Pennsylvania study coordinator to ensure they are properly being featured and not causing inappropriate comments. This monitoring will occur bi-weekly. If any problems arise with the social media ad they will be immediately removed however this is not anticipated as they are one-way ads. This type of advertising has been previously used for studies within the department and has been well received.

IRB Approval

It is expressly acknowledged that all informational material that could be construed to be advertising will be approved by the central IRB prior to dissemination.

Procedures for Tracking Sources of Subjects and their Disposition

We will track all contacts from subjects interested in the study. We will develop a pre-screening list that documents date and point of contact, eligibility based on telephone screening or survey, and follow-up if subject meets prescreening and is interested in further participation. The consent form may be mailed or emailed prior to the screening visit which is the next point of contact.

Obtaining Informed Consent

Once potential women have been prescreened, they will be referred to the site clinical coordinator or his/her designee for a screening visit. The consent process will be conducted according to each site's standard operating procedures.

Inclusion and exclusion criteria will be reviewed. After the study has been completely explained to the woman, she will be given the informed consent documents to review. Some individuals may wish to complete the informed consent process at the time of this discussion. In these cases, the informed consent documents will be signed once all questions are resolved. In other cases, the subjects may wish to take the consent forms home for further consideration. In these cases, the coordinator will confirm the woman's willingness to be contacted, and set up a tentative timeframe to be back in touch with the subjects. The consent can be signed once all questions have been answered to the satisfaction of the potential subject. A signed informed consent document, approved by the central IRB, will be confirmed on all subjects prior to the baseline evaluation.

In order to be eligible for enrollment and randomization, the woman must be confirmed to meet all inclusion and exclusion criteria described above.

Intervention Group Assignment

After screening is completed the information will be uploaded in RedCAP electronically, and randomization will be performed by IDS at the time of the randomization visit. Subjects and study coordinators will not be informed of their treatment assignment.

Study Interventions

Interventions, Administration and Duration

Study Medication: All subjects will be randomized to receive either OCP + placebo, Metformin + placebo or OCP + Metformin for 24 weeks. All medications will be self-administered. Once eligibility has been confirmed and subjects have been randomized, the site staff will distribute appropriate medications during each visit. The subject will receive enough pills to last until the next visit (additional pills for each arm will be distributed at the start of the study for situations if/when the visit window must be utilized; subjects will receive appropriate instructions regarding the extra medication). Subjects will be required to wash out of any excluded medications prior to enrollment in the study.

Medication Compliance: Medication bottles will be returned at visits 3 through 6 unless a remote visit is being conducted at the discretion of the PI. IDS will perform pill reconciliation during these visits to measure medication compliance. Medication compliance can also be assessed by reviewing the returned subject diaries. Compliance is assessed during the monthly visits on site or remote contact with the subject. Non-compliant subjects will be reminded of the importance of taking the medication properly.

Life Style Modification (LSM): In addition to taking study medication, all subjects will receive counseling (through the use of handouts) about diet and exercise at the randomization and 16 week visit. The diet is based on the lifestyle modification protocol of the look AHEAD study and POWER-UP trial. The study will follow the Diabetes Prevention Program recommendations for increasing physical activity. A similar protocol was utilized in OWL-PCOS and similar written materials will be provided to all subjects in the current trial. Assessment of dietary intake will be based on NCI created automated self-administered 24-hour (ASA24) food recall tool. This will allow us to access variability in dietary intakes in the 3 arms of the study.

Cognitive Testing: All subjects will undergo cognitive functioning testing via the NIH Toolbox, a comprehensive set of neuro-behavioral measurements that quickly assesses cognitive, emotional, sensory, and motor function. Audio-recording of cognitive testing is optional (all recordings will be deleted after transcription). The NIH Toolbox is assessing cognition for subject (age3-85), thus eliminating a ceiling effect. Staff will be trained to administer the tests. Training is performed online via the NIH Toolbox website. Any additional training or oversite will be done by a Clinical Neuropsychologist. During testing staff will audio record cognitive testing with subjects to verify answers given in a timely matter. All audio recordings will be consented for by the subject prior to recording and will remain on file for less than 24 hours at which point they will be deleted. One patient recording from each certified staff member will go to the Clinical Neuropsychologist to verify standardization. A description of the neuropsychological assessments includes:

Neuropsych assessments:

- Controlled Oral Word Association (COWA): subjects must spontaneously name as many words as possible beginning with a given letter within a 60 second span.
- *Category fluency:* subjects must spontaneously name as many objects as possible that fit a given category within a 60 second span.
- Logical memory: subject is read the first story and recalls as many details as possible. The subject is then read a second story and must recall as many details as possible about that story; second story and recall is repeated. Following a delay of 25-35 minutes, the subject must again recall as many details of each story as possible.
- *Digit Span:* subject is read a string of numbers and must repeat the numbers back to the examiner in either the exact same order (DS forward) or in reverse order (DS backward). Number strings increase in length by one number with each successful turn, and discontinued when patient makes an error. Score is the longest string a patient can successfully repeat back.
- *Digit symbol substation:* Testing page shows a key at the top, which contains the numbers 1-9, each paired with a special symbol. Below the key, subjects must fill in the numbers that match a grid of special symbols as quickly as possible, based on the key above.
- *Rey-Osterreith Figure:* subject copies the complex figure from the stimulus page. The stimulus is removed and the patient then immediately redraws as much of the figure as they can (immediate recall score).
- *Pegboard:* subject is tested with both dominant and non-dominant hands on how quickly they can fill in a pegboard. Each peg has a groove, which must be perfectly matched with the groove of the hole in order to fit. Score based on time to complete.
- *Trail making:* Numbers are scattered over a page and the subject must connect the numbers in numerical order; score derived from both number of errors and time to complete. Executive function can be tested by requiring patients to connect numbers in an alternating fashion between two colors, i.e. yellow 1-pink 2-yellow 3- pink 4, etc. Score still derived from both errors and time to complete.
- *Visual Puzzles:* Subjects are shown a 2D item that they are to imagine as a puzzle made from 3 pieces. The subject indicates which 3 pieces fit next to each other without stacking to make the given item. Each item has a 30 second time limit, with a discontinuation rule of 3 errors in a row. The score is based on time and errors.

Urine Pregnancy Test: A urine pregnancy test will be performed for all subjects at every visit. If a positive result is found, the subject will be informed by site staff of positive result and offered resources regarding prenatal care or alternative options. In the case of a positive pregnancy result, subjects will be withdrawn from the study. In the case of a subject becoming pregnant, the subject will have the choice to consent to allow the study team to track until outcome of the pregnancy.

Vital Signs and Biometrics: Vital signs and biometrics for this study include but are not limited to, measuring height and weight, blood pressure, pulse, waist and hip circumference. Vital signs and biometrics will be collected at every visit except height which will only be recorded at the screening visit. Blood pressure and pulse will be measured in sitting position at all visits after the subject has rested for at least five minutes. Three blood pressure measurements will be taken 5 minutes apart and then averaged.

Laboratory Evaluations: Blood will be collected at Screening, Randomization, week 16 and week 24 visits (early termination visit). Subjects will be required to be fasting prior to Screening, Randomization, week 16 and week 24 visit (nothing to eat or drink besides water for a minimum of 8 hours prior to blood draw). Subjects who have used hormonal contraception must wait at least 30 days prior to the collection of screening and fasting blood I tests. Screening blood tests that were completed within the last year can be substituted for laboratory tests collected at screening visit.

Transvaginal Ultrasound: Transvaginal ultrasound examinations will be performed at screening if indicated, randomization and 24 week visit (or early termination visit). The transvaginal ultrasound examinations will be performed according to the standard procedure for the center and include finding regarding the uterus, the endometrium and the ovaries. If a transvaginal probe is not tolerated, then transabdominal ultrasound may be used. The same procedures were used in the OWL-PCOS study and are well known by the centers.

F-G Score: The Ferriman-Gallwey score is a measure for quantifying hirsutism in women. The Primary Investigator (or designee, which may be the subject) will assess each subject's hirsutism using the Ferriman-Gallwey scale at Screening, Randomization (if applicable and/or necessary) and 24 week visit. During the assessment for hirsutism, the PI (or designee) will also assess the subject's acne.

DXA: DXA scans will be completed on each patient at Randomization Visit and 24 week visit. The scanning will include a whole body scan, the lumbar spine and both hips.

Oral Glucose Test: OGTT will be performed at the randomization and at 24 week visit. Prior to the OGTT subject must fast overnight for minimum of 8 hours. If subject is not fasting, the blood work must be rescheduled. Patients will receive 75 g of an oral glucose solution at time zero (0) and blood will be sampled every 30 minutes for 2 hours for glucose, and insulin levels.

PCOSQ: The PCOSQ is a self-administered questionnaire for measuring health-related quality of life in women with PCOS. The PCOSQ will be administered to subjects at Randomization and 24 week visit.

STAI: The STAI (State-Trait Anxiety index) is a questionnaire for accessing trait anxiety and state anxiety. The STAI will be administered to subjects at Randomization and 24 week visit.

CES-D: The CES-D is a screening test for depressive symptoms. The CES-D will be administered to subjects at Randomization and 24 week visit.

FSDS-R: The FSDS-R (The Female Sexual Distress Scale-Revised) is a screening questionnaire for measuring sexually related personal distress in women with Female Sexual Dysfunction (FSD)

FSFI:The FSFI (Female Sexual Function Index) is a brief questionnaire measure of sexual function in women. ItCOMET-PCOS PROTOCOL V10.1NOVEMBER 30, 2021

was developed for the specific purpose of assessing domains of sexual function (e.g. sexual arousal, orgasm, satisfaction, pain) in clinical trials.

ASA24: The Automated Self-Administered 24-Hour Dietary Assessment Tool (ASA24). This 24-hour dietary recall captures detailed information about all foods, drinks, and supplements (including vitamins, minerals, herbals, and other dietary supplements) you consumed from midnight to midnight. You will be asked to complete this at 12 weeks and 24 weeks.

Concomitant Interventions

No other interventions, other than those specified in the protocol are allowed to treat PCOS or weight management during participation in the study.

Adherence Assessment

Adherence to the interventions will be monitored by the use of medication reconciliation, diary compliance and by monthly visits on site or contact with the subject.

Clinical and Laboratory Evaluations

Schedule of Evaluations

The table below summarizes the clinical and laboratory evaluations during the trial. A description of the visits follows. Note, prior to the screening visit, subjects may prescreen for potential eligibility.

Study Visit Schedule	Screening (half of the visit as a remote option)	Randomization	Randomization Patient Contact (PC)	4 Week Visit (remote option)	8 Week Visit (remote option)	12 Week PC	16 Week Visit	20 Week PC	24 Week Visit	Early Termination Visit (> or equal to 12 weeks of medication)	End of study PC
Sign Informed Consent	x										
Medical History Questionnaire	x										
Screening labs	x*										
DNA Sample		х									
Safety Labs	x*	х					x		x	x	
Menstrual History	x	х		x	x		x		x	x	
Urine Pregnancy Test	x	х		x	x		x		x	x	
Vitals and Biometrics	x	х		x	x		x		х	x	
Hirsutism Assessment	x	х							x	x	
Transvaginal Ultrasound	x*	х							x	x	
Fasting labs		х					x		x	x	
OGTT labs		х							x	x	
DXA Scan		х							x	x	
Lifestyle Modification		х					х				
ASA 24						x			х	x	
Acne Assessment		х							х	x	
HRQOL – PCOS, STAI, CES-D, FSDS-R, FSFI &		х							x	x	

Table 6: Study Visits and Procedures

Cognitive testing Questionnaires											
Randomization		х									
Dispense Medication/Log		x		x	x		х				
Collect Medication/Log				x	x		x		х	х	
Review Concomitant Medications	x	х	х	x	x	x	x	x	x	x	x
Review Adverse Events			x	x	x	х	х	х	х	х	x

*As Needed

Timing of Evaluations

7.2.1 Screening visit:

- 1. Obtain informed, signed consent from subject.
 - Subject must specifically be made aware of potential drug side effects and adverse outcomes.
 * Remote option for e-consent via REDCap, utilization of this option at PI discretion
- 2. Complete medical assessment.
 - At the Screening Visit, a detailed general medical history for the former 6 months (longer in case of gynecological relevance) and history of concomitant diseases or interventions is to be reviewed and to be documented.
 - * Remote option for completion, utilization of this option at PI discretion
- 3. Must obtain and record menstrual history.
 - Determine need for medroxyprogesterone acetate (if subject has had no menses in the last 3 months)
 - * Remote option for completion, utilization of this option at PI discretion
 - 4. Perform urine pregnancy test.
 - 5. Record vital signs and biometrics
 - 6. Blood draw for both screening labs (as needed) and safety labs (as needed)
 - Review Hirsutism (F-G) Score
 * Remote option for completion, utilization of this option at PI discretion
 - 8. Transvaginal Ultrasound (if indicated)
 - 9. Review electronic Medical Record (if available)
 - If subjects are patients through the University of Pennsylvania Health System or Hershey Medical Center, electronic medical records will be reviewed to verify eligibility. Screening blood laboratory tests that were completed within the last year can be substituted for laboratory tests collected at screening and randomization visit.

Table 7: Screening Blood Tests

Category	Tests		
Safety Labs**	Complete metabolic panel, lipid profile		
Screening Labs	TSH*, Prolactin*, HbA1c*, CBC*, 17OH Progesterone^, DHEAS^,		
	Total Testosterone [#] ,		

*If drawn within 1 year of screening, eligible for use to determine eligibility criteria.

^ If drawn within lifetime prior to screening, eligible for use to determine eligibility criteria.

If FG≥6 (≥2 for women of Asian descent) do not need to draw lab. Eligibility criteria can be determined without this lab value.

** If drawn within 2 months of screening, eligible for use to determine eligibility criteria. These safety labs must be drawn at Randomization visit if not drawn at Screening visit.

7.2.2 Randomization Visit:

- 1. Review menstrual history
- 2. Complete urine pregnancy test
- 3. Record vital signs and biometrics
- 4. Complete fasting blood draw and Safety labs (as needed)
- 5. Optional whole blood draw for DNA testing
- 6. Start the oral Glucose Tolerance Test (this may be first since the subjects are fasting)
- 7. Review Lifestyle Modification Counseling
- 8. Complete PCOSQ, CESD-R, STAI, FSDS-R & FSFI
- 9. Cognitive testing
- 10. Complete DXA scan
- 11. Transvaginal Ultrasound (if indicated)
- 12. Randomize into study arm
- 13. Dispense Logs/Medications
 - Review medication instructions

*For more detailed information regarding the order in which study procedures should occur, please refer to the Manual of procedures.

*Complete patient contact with subject two weeks after this visit. COMET-PCOS PROTOCOL V10.1 NOVEMBER 30, 2021

Category	Tests		
Fasting blood Labs	Total and free T, Apo A, Apo B, Apo.C3, hsCRP, FFA, IL-1,IL-6,1L- 10, hsCRP, NMR lipoprotein analysis, HDL-C efflux, AMH, SHBG, TNF alpha, Estradiol		

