The primary analysis will use an intent-to-treat paradigm, wherein all randomized subjects are included according to their randomized treatment arm. Data will be summarized using descriptive statistics for continuous variables and frequency statistics for categorical variables. For the primary outcome of the presence of MetS at the end of the trial, logistic regression will be used with independent variables that include terms for the treatment arm and the 3 randomization stratification factors as covariates, with a contrast constructed to test for linear trend over the three treatment arms. For secondary continuous outcomes, linear mixed-effect models will be fit to assess differences between the treatment arms with respect to changes in these outcomes over time. The independent variables in the model will be treatment arm, time, the interaction of treatment and time and the 3 randomization factors as covariates.

Anticipated time to completion

A total of 5 years (2017-2022) is anticipated. 3.5-year enrollment period (based on 3 subjects per site/month x 2 sites), 6-month treatment period followed by time for analyses and interpretation of the data.

Regulatory Compliance

A data safety and monitoring board, led by [name], has been established to ensure that patient safety and clinical study data and regulatory requirements are met regarding the Food and Drug Administration (FDA) code for federal regulations. This trial is registered on http://www.clinicaltrials.gov

Study Objectives

Primary Aim

Our primary goal is to determine the effect of 6 months' treatment with OCP vs. metformin vs. OCP + metformin on prevalence of MetS and its components in overweight / obese women. Implicit in the primary aim is clearly defining MetS, by NCEP ATPIII criteria as the presence of at least 3 of the following 5 criteria: TG≥150mg/dl, HDL-C<50mg/dl, BP≥130/≥85mmHg, WC>88cm and fasting glucose≥100mg/dl; and the goal of tracking safety of our interventions throughout the study (through safety lab evaluations, vital signs and diaries).

Secondary Aim

The study will assess secondary outcomes such as defining the effects of OCP (lowering androgens) verses metformin (improving insulin sensitivity) verses OCP + metformin on body fat distribution, glucose tolerance, adipokines and markers of inflammation.

- 1. Assess change in HDL-C function by measuring reverse cholesterol efflux capacity.

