- 1. Both MetS and PCOS are major health problems and the risks of common treatments (OCP or metformin) on development of MetS are poorly understood.
- 2. Knowledge gained from this investigation will identify optimal strategies for treatment of overweight/obese women with PCOS
- 3. Understanding the underlying pathophysiology for alterations in metabolic risk with OCP or metformin use, will provide important information for future studies.

Statistical Considerations

General Design Issues

This will be a randomized, double-blind, double dummy clinical trial of three types of medication, OCP + placebo, metformin + placebo or OCP + metformin. We will track all subjects to completion. Subjects will be randomized 1:1:1 to the three treatments.

Randomization

Randomization is a critical feature of a clinical trial because it prevents treatment-selection biases. The study statistician will develop the programs for the randomization; however, the final random seeds used to generate the randomization scheme will be prepared by a statistician in PSU's Department of Public Health Sciences independent of the study in order to keep the study statistician blinded as well. The randomization scheme for this study will use variable-size, random permuted blocks to ensure that the number of participants in each treatment arm is balanced after each set of *B* randomized participants, where *B* is the block size. Furthermore, the randomization will be stratified by recruitment site (UPenn/PSU), race (AA/non-AA), and the presence of MetS at baseline (yes/no). Randomization to the metformin or OCP arms will use 1:1:1 allocation.

Outcomes

Primary Outcome Measurements

The primary outcome for this trial is prevalence of MetS.

Secondary Outcome Measurements

We may assess change in HDL-C function, serum apolipoproteins, lipid particle size and number, body fat distribution, BMI, serum adipokines, HbA1c, glucose and insulin sensitivity, serum markers of inflammation, free fatty acids, androgens, quality of life parameters, cognitive testing and predictive factors for change in prevalence on MetS

Sample Size and Accruals

Sample Size and Power Calculations

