Primary analyses will invoke an intent-to-treat paradigm, wherein all randomized subjects are included according to their randomized treatment arm, regardless of actual treatment received, protocol violations, etc. Data will be summarized using descriptive statistics for continuous variables (mean, standard deviation, number of observations, and percentiles) and frequency statistics (frequencies and percentages) for categorical variables. The area under the curve (AUC) for glucose and insulin from the OGTT will be calculated using the trapezoidal rule. Univariate and bivariate distributions will be inspected in order to address any missing data, inconsistent responses, outliers, and data entry errors. The sample size estimates have taken into consideration a participant drop-out of 15%; however, every effort will be made during the studies to minimize any drop-out. If, however, study attrition appears to be an issue, we will use the observed data to determine if patients who completed the study differed from those who did not. To control for potential confounding factors for the association of the treatment effects with the metabolic syndrome, we have stratified the randomization by recruitment site, race, and the presence of metabolic syndrome at baseline. Although stratification may potentially yield unequal numbers between strata, within each individual stratum there will be approximately equal numbers and balance between treatment groups. All analyses will include these 3 randomization stratification factors as covariates in the statistical models. All hypothesis tests will be two-sided and all analyses will be performed using SAS software, version 9.4 (SAS Institute, Inc., Cary, NC), R software (open source), or Stata software, version 13 (StataCorp LP, College Station, TX).

For the primary outcome of the presence of the metabolic syndrome at the end of the 6-month trial, logistic regression will be used with independent variables that include terms for the treatment arm and the 3 randomization stratification factors as covariates, with a contrast constructed to test for linear trend over the three treatment arms.

A variety of secondary continuous outcomes will be collected during this longitudinal trial. These secondary outcomes include serum androgens, cholesterol efflux (HDL-C function) parameters, serum apolipoproteins, lipid particle size and number, anthropometric measures (BMI, adipokines, biomarkers of inflammation (e.g., hsCRP),

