measures of adipose tissue, abdominal adiposity, and quality of life measures (PCOSQ). For these continuous outcomes, linear mixed-effects models will be fit to assess differences between the treatment arms with respect to changes in these outcomes over time. The independent variables in the model will be treatment arm, time, the interaction of treatment and time, and the 3 randomization stratification factors as covariates. From the mixed-effects models, contrasts will be constructed to test the hypotheses of interest with respect to changes over time in the outcomes. Linear mixed-effects models are an extension of ordinary regression models that account for the between- and within-subject correlation inherent in longitudinal trials. Further, linear mixed-effects models do not drop patients with incomplete data and are easily extended to nonlinear mixed-effects models for ordinal data and count outcomes. Following our assessment of the initial fit of the models, we will add covariates to the models that correspond to other potential confounders (e.g., age) to assess their impact, if any, on the treatment effects. Residual diagnostics will be assessed to determine the appropriateness of the model fit and, if necessary, transformations of the response will be used to quantify the magnitude of the effects.

For any binary outcomes collected at each visit, analyses will be based on generalized estimating equations (GEE) with a logit link, an extension of logistic regression that accounts for correlated data within-subjects inherent in longitudinal trials, with independent variables that include terms for the treatment arm, time, the interaction of treatment and time, and the 3 randomization stratification factors as covariates. Following our assessment of the initial fit of the models, we will add covariates to the models that correspond to other potential confounders (e.g., age) to assess their impact, if any, on the treatment effects. The effect size will be quantified using the odds ratios (OR) and corresponding 95% CI.

Accrual

A total of 5 years will be required to complete the study after start up; 36-month enrollment period (based on 3 subjects per site/month x 2 sites), 1-month screening/randomization period, 6-month treatment period and time built in for data analysis and interpretation.

Data Collection, Monitoring and Adverse Experience Reporting

Records to be kept

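### In the mixed models for secondary outcomes, the stratification factors have no time interaction, so they barely touch the change-over-time contrast, and a check on age added the same way would be nearly uninformative

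*Combined protocol and SAP*

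**What the plan says.** The synopsis (Statistical Analysis) gives the fixed effects for secondary continuous outcomes: "The independent variables in the model will be treatment arm, time, the interaction of treatment and time and the 3 randomization factors as covariates". The Statistical Analysis text under Statistical Considerations repeats the list. Neither place names a covariate-by-time term or the outcome's own baseline value.

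The hypotheses are about change: "contrasts will be constructed to test the hypotheses of interest with respect to changes over time in the outcomes".

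The same section makes a general commitment: "All analyses will include these 3 randomization stratification factors as covariates in the statistical models". Under Randomization (9.2) the factors are site, race and MetS status at baseline, all fixed before treatment.

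After the initial fit the team will "add covariates to the models that correspond to other potential confounders (e.g., age) to assess their impact, if any, on the treatment effects". The plan does not say whether such covariates enter as main effects or with a time interaction.

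On missing data it notes that "linear mixed-effects models do not drop patients with incomplete data", and the sample-size text expects 15% dropout.

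**The concern.** The plan presents the stratification factors as adjusting the treatment comparison, and the added covariates as showing whether that comparison is sensitive to confounding. Both uses require the covariates to be able to move the tested contrast. In a model for repeated values, a term that is constant across a woman's visits describes her level and not her change.

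Two things are at stake. The intervals for change would take almost no account of the stratified randomization. And a treatment effect that stays put when age is added could be reported as evidence of robustness, when the model as specified could hardly have shown anything else.

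**Working it through.** **The plan's own figure.** The documents give no power or precision figure for the mixed models. The 80% power statement concerns the primary outcome and is not in question.

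**Step 1. Is baseline a response row?** Table 6 and the procedure descriptions schedule DXA, OGTT and PCOSQ at randomization and week 24 (or early termination) only. With one post-baseline visit, time and arm-by-time can be estimated only if baseline is among the responses. For fasting-blood outcomes (weeks 16 and 24) and BMI (every visit), this is the natural reading but not the only possible one.

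**Step 2. Algebra.** For woman i at visit t:

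Y(i,t) = arm + time + arm×time + x(i)·β + b(i) + e(i,t)

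where x(i) holds site, race and baseline MetS. Her change is

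Y(i,1) − Y(i,0) = [time and arm×time differences] + e(i,1) − e(i,0).

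The term x(i)·β is gone. With complete data and arm-by-time saturated, the contrast and its SE do not depend on x. This holds for random-intercept and unstructured covariance alike and needs no assumed variances. If the coefficient may differ by visit, x(i)·[β(1) − β(0)] stays in the change and the adjustment acts.

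**Step 3. Numerical illustration.** One simulated data set: 204 women (240 × 0.85), two visits, with age made to drive change and to be unbalanced between arms.

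| Covariates | Arm×time estimate | SE |
|---|---|---|
| None | 0.22846 | 0.1644 |
| Strata, main effects | 0.22846 | 0.1644 |
| Strata + age, main effects | 0.22846 | 0.1644 |
| Strata × time | 0.2202 | 0.1642 |
| Strata and age × time | 0.2056 | 0.1577 |

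**Step 4. With dropout.** Assumed effects and variances; 240 women, three arms, baseline and weeks 16 and 24, 40 data sets per setting. Entries are the mean absolute shift of the week-24 arm-by-time estimate from the model without covariates, in SE units.

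| Setting | Strata | Strata + age | Strata and age × time |
|---|---|---|---|
| Complete, covariates do not predict change | 0 | 0 | 0.10 |
| Complete, covariates predict change | 0 | 0 | 0.28 |
| 15% random dropout | 0.03 | 0.05 | 0.10 |
| 15% covariate-dependent dropout, covariates predict change | 0.04 | 0.08 | 0.34 |
| 30%, otherwise as above | 0.04 | 0.08 | 0.35 |

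A two-visit version with 15% random dropout gave 0.03, 0.05 and 0.13. At 15% dropout, main effects changed the SE by a factor of 0.997 to 0.999.

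**Step 5. Precision.** Let r be the correlation of baseline MetS with the baseline outcome and ρ the correlation between visits. Both are assumptions; the documents give neither. If MetS is related to change only through the baseline value (regression to the mean), its share of the variance of change is R² = r²(1 − ρ)/2, and the SE as planned is too large by 1/√(1 − R²).

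- r = 0.3: ρ = 0.7 gives R² = 0.0135 and 0.7%; ρ = 0.5 gives 0.0225 and 1.1%.
- r = 0.5: ρ = 0.7 gives 0.0375 and 1.9%; ρ = 0.5 gives 0.0625 and 3.3%.
- r = 0.7: ρ = 0.7 gives 0.0735 and 3.9%; ρ = 0.5 gives 0.1225 and 6.8%.

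The nominal 5% test then runs at about 4.3-4.9% for r of 0.3 to 0.5, and at about 3.6% in the last case.

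**The case against.** A reader might infer that the adjustment does nothing at all and that the confounder check must always show no impact. The documents do not support that. The cancellation is exact only with complete data, and the plan expects dropout and keeps partial records, so estimates move a little. The form of the added confounders is also unstated, and a time-varying covariate would not cancel. What stands is that the only form the plan shows is a main effect, and its named example is age.

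For outcomes with several post-baseline visits, change from baseline could be the response, and stratum main effects would then adjust. The text does not exclude this. It does not state it either, and it does not work for DXA, OGTT or PCOSQ.

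The commitment covering all analyses is literally kept, since the factors are in the models. Its stated motive concerns confounding for MetS, which is the primary outcome, and in that logistic model the strata do adjust. This is a fair limit on the point, though the same sentence is applied to the secondary models, where the factors have almost no effect on what is tested.

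The precision loss is small and partly double-counted. With 30% MetS prevalence, a dichotomised normal variable correlates at most 0.76 with its own underlying variable, so r = 0.7 is extreme for most of these outcomes. In a simulation at r = 0.7 and ρ = 0.5 where MetS acts only through the baseline value, adding MetS after adjusting for the baseline outcome changed the SE by a factor of 1.000.

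The age illustration is constructed. Randomization gives no expected imbalance, and a difference of 0.3 SD between two arms of 68 to 80 women arises by chance in about 6-8% of comparisons (0.3/√(2/68) = 1.75; 0.3/√(2/80) = 1.90). It shows what the check would miss, not what is likely to happen.

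**Conclusion.** The point holds in limited form. With baseline as a response row, the listed stratum terms cancel exactly from the arm-by-time contrast when data are complete, and shift it by about 0.03-0.04 SE at 15% dropout under the simulated conditions. Adding age as a main effect brings the shift to 0.05-0.08 SE, so the check would be nearly uninformative in that form. The complete-data result is an identity; the dropout and precision figures depend on assumed variances and correlations.

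The consequence for inference is modest and conservative: an SE about 1-3% too large for r of 0.3 to 0.5, and up to about 7% under stronger assumed correlations, much of which adjusting for the baseline outcome would also recover.

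A reader might go on to infer that the secondary treatment effects are biased or that the primary result is in doubt. Neither follows. Randomization protects the contrast, no bias is shown, and the primary logistic model adjusts a week-24 outcome directly. The algebra is also not exact for the logit GEE models, so the point is confined to the linear mixed models.

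**What to change.** In the synopsis and in the Statistical Analysis text for secondary continuous outcomes, either add site × time, race × time and baseline MetS × time to the model, or define the response as post-baseline values or change, with these factors and the baseline outcome as covariates. State which rows are responses. State also that any further baseline covariate, such as age, enters with its time interaction in the first form. The arm comparisons being tested stay as they are.

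The cost is 3 degrees of freedom per post-baseline visit for the interaction form, with no new data or patients. In the complete-data simulations, strata and age by time changed the SE by a factor of 1.008 when the covariates did not predict change and 0.98 when they did, so the price of an unneeded term is small.
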